## 10.3 Technical Details for Pharmacokinetic Statistical Analysis

### 1) Exclusion of Data

The following data will be rejected and excluded from pharmacokinetic analyses:

- [REDACTED]
- Plasma drug concentrations after use of prohibited concomitant medications or foods that may affect the PK of brexpiprazole, and pharmacokinetic parameters calculated using rejected concentrations
- Plasma drug concentrations after failure to receive the IMP according to the conditions specified in the protocol (Section 5.3.1 and Section 6.1.2), and pharmacokinetic parameters calculated using rejected concentrations
- Plasma drug concentrations in samples collected outside the protocol-specified acceptable window (Table 1.3-2) of blood sampling time points. These data will be excluded from the calculation of descriptive statistics of concentrations at the time points, but will be used for the calculation of pharmacokinetic parameters.
- Plasma drug concentrations and pharmacokinetic parameters in a period for compounds for which the predose plasma drug concentrations exceed 5% of  $C_{max}$  during that period
- Plasma drug concentrations or pharmacokinetic parameters judged to be inappropriate by the clinical pharmacologist for other reasons than the above. In this case, the reason for judging them to be inappropriate will be recorded.

## **2) Handling of Data below the Lower Limit of Quantification**

- Plasma drug concentrations below the lower limit of quantification will be regarded as 0 ng/mL when they occur prior to the first measurable concentration in each period and as missing when they occur after the measurable concentration.

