## 5.3 Handling of Missing Data

No imputation procedures will be applied for missing data.

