### 2) Statistical Analysis Methods

Descriptive statistics will be calculated as described below. However, if more than half of the subjects in an analysis set are excluded from summarization due to missing values, not calculable, or rejected data, descriptive statistics to be calculated for that parameter will include only the number of subjects in the analysis set and the number of subjects tabulated.

- a) Plasma drug concentration
  - For 1) a), descriptive statistics will be calculated at each blood sampling time point excluding the withdrawal and unscheduled time points by meal condition and compound.
  - The descriptive statistics to be calculated will include the number of subjects in the analysis set, the number of subjects tabulated, arithmetic mean, standard deviation, coefficient of variation, minimum, median, and maximum.
- b) Plasma PK parameters (except for  $\lambda_z$ )
  - For 1) b), descriptive statistics will be calculated by meal condition and compound.
  - For 1) c), descriptive statistics will be calculated by meal condition.
  - The descriptive statistics to be calculated will include the number of subjects in the analysis set, the number of subjects tabulated, arithmetic mean, standard deviation, coefficient of variation, geometric mean, minimum, median, and maximum. However, descriptive statistics to be calculated for  $t_{max}$  and  $t_{last}$  will be the number of subjects in the analysis set, the number of subjects tabulated, minimum, median, and maximum.

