PKF-2.1	Median Brexpiprazole Plasma Concentrations Following Single Oral Administration of Brexpiprazole QW Formulation (Food Effect Analysis Set)
PKF-2.2	[REDACTED]
PKF-3.1	Individual Brexpiprazole Plasma Concentrations Following Single Oral Administration of Brexpiprazole QW Formulation (Food Effect Analysis Set)
PKF-3.2	[REDACTED]
PKF-4.1	Individual Brexpiprazole Plasma Concentrations Following Single Oral Administration of Brexpiprazole QW Formulation for Test Group in Comparison to Reference Group
PKF-4.2	[REDACTED]

[figure not shown]

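### Setting late below-limit concentrations to missing in the time-point summaries as well as in the PK parameters makes any affected late median, mean and minimum too high

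*SAP*

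**What the plan says.** SAP 10.3 item 2) has a single rule with two halves, applied period by period. The first half is "Plasma drug concentrations below the lower limit of quantification will be regarded as 0 ng/mL when they occur prior to the first measurable concentration". The second half treats below-limit values "as missing when they occur after the measurable concentration". The rule stands among the technical details for PK statistical analysis in general. It draws no line between computing parameters and summarising concentrations. Item 1) of the same section does draw that line for samples taken outside their time window: they leave the time-point summaries but stay in the parameters.

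SAP 5.3 adds "No imputation procedures will be applied for missing data". For plasma concentrations, SAP 10.2 item 2) says "descriptive statistics will be calculated at each blood sampling time point excluding the withdrawal and unscheduled time points by meal condition and compound", and the statistics are "the number of subjects in the analysis set, the number of subjects tabulated, arithmetic mean, standard deviation, coefficient of variation, minimum, median, and maximum". If more than half of an analysis set is "excluded from summarization due to missing values, not calculable, or rejected data", only the two counts are shown. SAP Appendix 4 lists a mean figure (PKF-1.1) and a median figure (PKF-2.1) of brexpiprazole concentrations.

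**The concern.** A trailing below-limit result is not lost information. It tells the analyst that the concentration is lower than every value that could be measured. Setting it to missing removes the subject from that time point because the value is low. Early time points then cover everyone, with zeros, while late ones cover only subjects with enough drug left to measure. The printed minimum can never fall below the limit.

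For the parameters this does no harm. The protocol defines AUCt as running to the last observable concentration, so trailing below-limit values do not enter it. For the summaries nothing forces the exclusion: the concentration statistics include no geometric mean, and all of them can be computed with a value of zero.

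What is at stake is a declared secondary PK endpoint, plasma concentration of brexpiprazole and its metabolite, summarised by meal condition. Anyone comparing the late fed and fasting profiles would be comparing two groups selected to different degrees.

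**Working it through.** The plan states no figure on this point, so there is nothing to reproduce. The check asks how far the printed summaries move.

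**Inputs from the documents.** The below-limit rule and the list of statistics are as above. The last scheduled samples are at 240 and 312 hours (protocol Table 1.3-2). There are 36 planned completers (SAP 3.1).

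**Assumptions.** The readable text gives no quantification limit, late concentrations or expected share below the limit. I take log-normal concentrations at one late time point with a between-subject CV of 60%, so σ = √ln(1 + 0.6²) = 0.5545. A share p of 10%, 25% or 40% is below the limit.

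**One meal condition.** With z(·) the normal quantile and Φ the normal distribution function:

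- Printed median / true median = exp{σ · z((1 + p)/2)}. At p = 0.40 this is exp(0.5545 × 0.5244) = 1.34.
- Printed mean / true mean = Φ(σ − z(p)) / (1 − p). At p = 0.40 this is 0.790 / 0.60 = 1.32.
- With zeros, mean / true mean = Φ(σ − z(p)). The median is exact while fewer than half are below the limit.

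| Share below limit | Median, set to missing | Mean, set to missing | Median, ranked below limit | Mean, set to 0 |
|---|---|---|---|---|
| 10% | 7% high | 7% high | exact | 3% low |
| 25% | 19% high | 19% high | exact | 11% low |
| 40% | 34% high | 32% high | exact | 21% low |

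**Two conditions, same spread.** Take a true fed/fasting ratio of 1.5 with 40% of fasting values below the limit.

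- Share of fed values below it: Φ(−0.2533 − ln 1.5/0.5545) = Φ(−0.985) = 16.2%.
- Ratio of the medians under the current rule: 1.5 × 1.120/1.337 = 1.26.
- Ratio of the means under the current rule: 1.5 × 1.120/1.317 = 1.28.
- Counting the values below the limit restores the median ratio to 1.50.
- With zeros the mean ratio becomes 1.5 × 0.938/0.790 = 1.78.

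Over CVs of 30% to 80%, true ratios of 1.25 to 2.0 and 5% to 50% of fasting values below the limit, the current rule shrank the ratio in every equal-spread case.

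**Two conditions, unequal spread.** Take log-SD 0.3 fasting and 0.7 fed, equal true means, and 10% of fasting values below the limit. Then 39.6% of fed values are below it. The mean ratio reads 1.378/1.048 = 1.32 instead of 1.00, and the median ratio 1.13 instead of 0.82. The distortion is upward here.

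**The more-than-half rule.** With 36 subjects, 18 excluded is exactly half, so a mean and median based on the other 18 would still be printed.

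**The case against.** The strongest case against has five parts.

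1. *Below-limit values may be rare.* Nothing readable points to a large share at 240 to 312 hours. SAP 10.3 item 1) provides for predose concentrations above 5% of Cmax, and Period 2 dosing may fall between Day 30 and Day 36, so the plan allows for measurable drug about four weeks after a dose. AUC∞ is also a primary parameter, which presumes a usable terminal phase. This stands as a reason to call the size conditional. It does not show that such values are absent, and the rule also covers the metabolite.

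2. *The direction is not fixed.* A reader might infer that the rule always pulls the fed/fasting difference toward none. The documents do not support that: shrinkage needs similar spread in both conditions, and the unequal-spread case above goes the other way. A reader might also infer that a biased ratio will be printed. No fed/fasting ratio of concentrations is planned; the only listed ratio table, PKT-3, is for PK parameters. The ratios in the check are what someone would form by eye from the summaries.

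3. *The plan shows the attrition.* The number in the set and the number tabulated appear together, summaries stop when more than half are excluded, and individual concentrations are tabulated (PKT-1.1) and plotted (PKF-3.1, PKF-4.1). This stands in part. The number tabulated does not separate below-limit values from lost or rejected samples. When the stop rule applies, a real result, mostly below quantification, looks like absent data.

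4. *Zeros are no cure for the mean.* This stands. In the equal-spread example the mean ratio is 1.78 with zeros and 1.28 with the current rule, against a true 1.5. At CV 30% with 25% below the limit, the single-condition mean is 17% low with zeros and 11% high with the current rule.

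5. *A weekly interval ends at 168 hours*, so the last two samples lie beyond it. That is fair, and it limits the importance of the point.

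**Conclusion.** The point holds as a minor one. As written, the rule removes late below-limit values from the concentration summaries because they are low. Where such values occur, the printed median, mean and minimum are too high. Under the CV 60% log-normal assumption the median excess is 7%, 19% or 34% at 10%, 25% or 40% below the limit; with none below the limit it is zero. A late fed/fasting comparison made from these summaries is then distorted, typically toward no difference when spread is similar and possibly away from it when spread differs.

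A reader might infer that the food-effect conclusion is at risk. It is not: trailing below-limit values do not enter Cmax or AUCt, and AUC∞ is extrapolated from the last measurable concentration. The number tabulated and the more-than-half rule limit the problem but do not remove it.

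The case for counting these values is clear for the median and the minimum. For the arithmetic mean it is a choice between biases.

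**What to change.** In SAP 10.3 item 2), confine the missing rule to the calculation of PK parameters. Then add for the concentration summaries and figures:

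- Valid below-limit samples stay in the number tabulated and rank below the limit, for example as 0, for the median and minimum.
- They do not count as excluded in the more-than-half rule. That rule now refers to a parameter, so also say that it applies to each concentration time point.
- The number below the limit is printed by time point and meal condition.
- The median is the main summary in the tail.
- One convention for the arithmetic mean and SD is stated, 0 or half the limit, with a note that it biases the mean, since no substitution is unbiased there.

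The cost is a few sentences in the SAP, one derived variable and one extra count in the concentration tables. The PK parameters and the primary analysis do not change.

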## **3) Handling of Plasma Drug Concentrations at Withdrawal and Unscheduled Visits**

- If blood sampling for measuring plasma drug concentrations at withdrawal or unscheduled visits is performed outside the acceptable window of scheduled visits, the data will be handled as withdrawal or unscheduled visit data. In accordance with [Section 10.2 2\) a\)](#), descriptive statistics will not be calculated for plasma drug concentrations at withdrawal or unscheduled visits.
- If blood sampling for measuring plasma drug concentrations at withdrawal or unscheduled visits is performed within the acceptable window of scheduled visits and no data are available at the scheduled visits, the data obtained at the withdrawal or unscheduled visits will be handled as scheduled visit data.

## **11 Pharmacodynamic Analyses**

No pharmacodynamic analysis is planned.

## **12 Pharmacogenomic Analyses**

Listings of data on CYP2D6 phenotypes will be provided. The frequency distribution will be determined as described in [Section 7.2](#).

## **13 Other Endpoint Analyses**

[REDACTED]

[REDACTED]

[REDACTED]

[REDACTED]

[REDACTED]

[REDACTED]

## **14 Interim Analysis**

Not applicable.

## **15 Changes in Planned Analysis**

None.

## Appendix 1 Criteria for Identifying Laboratory Values of Potential Clinical Relevance

Laboratory Tests	Criteria
Chemistry	
AST (SGOT)	$\geq 3 \times$ upper limit of normal (ULN)
ALT (SGPT)	$\geq 3 \times$ ULN
Alkaline phosphatase	$\geq 3 \times$ ULN
LDH	$\geq 3 \times$ ULN
BUN	$\geq 30$ mg/dL
Creatinine	$\geq 2.0$ mg/dL
Uric Acid	
Men	$\geq 10.5$ mg/dL
Women	$\geq 8.5$ mg/dL
Bilirubin (total)	$\geq 2.0$ mg/dL
CPK	$\geq 3 \times$ ULN
Prolactin	$>$ ULN
Hematology	
Hematocrit	
Men	$\leq 37\%$ and decrease of $\geq 3$ percentage points from Baseline
Women	$\leq 32\%$ and decrease of $\geq 3$ percentage points from Baseline
Hemoglobin	
Men	$\leq 11.5$ g/dL
Women	$\leq 9.5$ g/dL
White blood count	$\leq 2,800/\text{mm}^3$ or $\geq 16,000/\text{mm}^3$
Eosinophils	$\geq 10\%$
Neutrophils	$\leq 15\%$
Absolute neutrophil count	$\leq 1,000/\text{mm}^3$
Platelet count	$\leq 75,000/\text{mm}^3$ or $\geq 700,000/\text{mm}^3$
Additional Criteria	
Chloride	$\leq 90$ mEq/L or $\geq 118$ mEq/L
Potassium	$\leq 2.5$ mEq/L or $\geq 6.5$ mEq/L
Sodium	$\leq 126$ mEq/L or $\geq 156$ mEq/L
Calcium	$\leq 8.2$ mg/dL or $\geq 12$ mg/dL
Glucose	
Fasting	$\geq 100$ mg/dL
Non-Fasting	$\geq 200$ mg/dL
Total Cholesterol, Fasting	$\geq 240$ mg/dL
Triglycerides, Fasting	$\geq 150$ mg/dL

## Appendix 2 Criteria for Identifying Vital Signs and Weight of Potential Clinical Relevance

Variable	Criterion Value a	Change Relative to Baseline a
Pulse Rate	> 120 bpm < 50 bpm	$\geq 15$ bpm increase $\geq 15$ bpm decrease
Systolic Blood Pressure	> 180 mmHg < 90 mmHg	$\geq 20$ mmHg increase $\geq 20$ mmHg decrease
Diastolic Blood Pressure	> 105 mmHg < 50 mmHg	$\geq 15$ mmHg increase $\geq 15$ mmHg decrease
Weight	-	$\geq 7\%$ increase $\geq 7\%$ decrease

aIn order to be identified as potentially clinically relevant, an on-treatment value must meet the “Criterion Value” and also represent a change from the subject’s baseline value of at least the magnitude shown in the “Change Relative to Baseline” column.

**Appendix 3 Criteria for Identifying ECG Measurements of Potential Clinical Relevance**

Variable	Criterion Valuea	Change Relative to Baselinea
Heart Rate	$\geq 120$ bpm $\leq 50$ bpm	increase of $\geq 15$ bpm decrease of $\geq 15$ bpm
PR	$\geq 200$ msec	increase of $\geq 50$ msec
QRS	$\geq 120$ msec	increase of $\geq 20$ msec
QTcF	$> 450$ msec (males and females)	

aIn order to be identified as potentially clinically relevant, an on-treatment value must meet the “Criterion Value” and also represent a change from the subject’s baseline value of at least the magnitude shown in the “Change Relative to Baseline” column.

## Appendix 4 List of Summary Tables

CT-1.1	Subject Disposition (All Subjects)
CT-1.2	Analysis Set (Randomized Subjects)
CT-2.1	Reasons for Discontinuation (Randomized Subjects)
CT-2.2	Reasons for Discontinuation by Period (IMP Administered Subjects)
CT-2.3	Reasons for Discontinuation by Food Condition (IMP Administered Subjects)
CT-3.1	Demographic and Baseline Characteristics (Food Effect Analysis Set)
CT-3.2	Demographic and Baseline Characteristics (Safety Analysis Set)
CT-4.1	Concomitant Medications Taken during IMP Administration Period (Safety Analysis Set)
CT-4.2	Summary of Major Protocol Deviations by Center and Type of Deviation (Randomized Subjects)
CT-7	Extent of Exposure (Safety Analysis Set)
CT-8.1	Overall Summary of Adverse Event (Safety Analysis Set)
CT-8.2.1	Incidence of TEAEs by System Organ Class and MedDRA Preferred Term (Safety Analysis Set)
CT-8.2.2	Incidence of Drug-related TEAEs by System Organ Class and MedDRA Preferred Term (Safety Analysis Set)
CT-8.3.1	Incidence of TEAEs by Severity by System Organ Class and MedDRA Preferred Term (Safety Analysis Set)
CT-8.3.2	Incidence of Drug-related TEAEs by Severity by System Organ Class and MedDRA Preferred Term (Safety Analysis Set)
CT-8.4.1	Incidence of TEAEs with an Outcome of Death by MedDRA System Organ Class and Preferred Term (Safety Analysis Set)
CT-8.4.2	Incidence of Drug-related TEAEs with an Outcome of Death by MedDRA System Organ Class and Preferred Term (Safety Analysis Set)
CT-8.5.1	Incidence of Serious TEAEs by System Organ Class and MedDRA Preferred Term (Safety Analysis Set)
CT-8.5.2	Incidence of Drug-related Serious TEAEs by System Organ Class and MedDRA Preferred Term (Safety Analysis Set)
CT-9.1	Listing of Deaths (Safety Analysis Set)
CT-9.2	Listing of Serious Adverse Events Other Than Death (Safety Analysis Set)
CT-10.1.1	Descriptive Statistics for Clinical Laboratory Test Results - Serum Chemistry (Safety Analysis Set)
CT-10.1.2	Descriptive Statistics for Clinical Laboratory Test Results - Hematology (Safety Analysis Set)
CT-10.1.3	Descriptive Statistics for Clinical Laboratory Test Results - Urinalysis (Safety Analysis Set)
CT-10.2.1	Shift Tables of Clinical Laboratory Test Results - Serum Chemistry (Safety Analysis Set)
CT-10.2.2	Shift Tables of Clinical Laboratory Test Results - Hematology (Safety Analysis Set)
CT-10.2.3	Shift Tables of Clinical Laboratory Test Results - Urinalysis (Safety Analysis Set)
CT-10.3	Shift Tables of Clinical Laboratory Test Results - Qualitative Urinalysis (Safety Analysis Set)
CT-10.4.1	Incidence of Potentially Clinically Significant Abnormalities in Laboratory Tests (Safety Analysis Set)
CT-10.4.2	Listing of Potentially Clinically Significant Abnormalities in Laboratory Tests (Safety Analysis Set)
CT-10.5.1	Incidence of Hy's Law Cases (Safety Analysis Set)
CT-10.5.2	Listing of Hy's Law Cases (Safety Analysis Set)
CT-11.1	Descriptive Statistics for Vital Signs (Safety Analysis Set)
CT-11.2.1	Incidence of Potentially Clinically Significant Abnormalities in Vital Signs (Safety Analysis Set)

[figure not shown]
CT-11.2.2	Listing of Potentially Clinically Significant Abnormalities in Vital Signs (Safety Analysis Set)
CT-12.1	Descriptive Statistics for 12-Lead ECG Parameters (Safety Analysis Set)
CT-12.2	Shift Table of 12-Lead ECG Findings (Safety Analysis Set)
CT-12.3	Incidence of Categorical Changes in 12-Lead ECG - QTcF (Safety Analysis Set)
CT-12.4.1	Incidence of Potentially Clinically Significant Abnormalities in ECG Evaluations (Safety Analysis Set)
CT-12.4.2	Listing of Potentially Clinically Significant Abnormalities in ECG Evaluations (Safety Analysis Set)
CT-13.1	Descriptive Statistics for Body Weight and BMI (Safety Analysis Set)
CT-13.2.1	Incidence of Potentially Clinically Significant Abnormalities in Body Weight (Safety Analysis Set)
CT-13.2.2	Listing of Potentially Clinically Significant Abnormalities in Body Weight (Safety Analysis Set)
CT-14	Descriptive Statistics for DIEPSS (Safety Analysis Set)
CT-15	Summary of Suicidality in C-SSRS (Safety Analysis Set)
CT-16.1	Listing of Subjects whose CGI-S has Worsened (Safety Analysis Set)
CT-16.2	Listing of Subjects whose CGI-I has Worsened (Safety Analysis Set)
PKT-1.1	Individual and Summarized Brexpiprazole Plasma Concentrations Following Single Oral Administration of Brexpiprazole QW Formulation (Food Effect Analysis Set)
PKT-1.2	[REDACTED]
PKT-2.1	Individual and Summarized Brexpiprazole Plasma Pharmacokinetic Parameters Following Single Oral Administration of Brexpiprazole QW Formulation (Food Effect Analysis Set)
PKT-2.2	[REDACTED]
PKT-3	Summary of Geometric Mean Ratio with Two-sided 90%CI for Brexpiprazole Pharmacokinetic Parameters (Food Effect Analysis Set)
PKF-1.1	Mean Brexpiprazole Plasma Concentrations Following Single Oral Administration of Brexpiprazole QW Formulation (Food Effect Analysis Set)
PKF-1.2	[REDACTED]
PKF-2.1	Median Brexpiprazole Plasma Concentrations Following Single Oral Administration of Brexpiprazole QW Formulation (Food Effect Analysis Set)
PKF-2.2	[REDACTED]
PKF-3.1	Individual Brexpiprazole Plasma Concentrations Following Single Oral Administration of Brexpiprazole QW Formulation (Food Effect Analysis Set)
PKF-3.2	[REDACTED]
PKF-4.1	Individual Brexpiprazole Plasma Concentrations Following Single Oral Administration of Brexpiprazole QW Formulation for Test Group in Comparison to Reference Group
PKF-4.2	[REDACTED]

[figure not shown]
## Appendix 5 List of Subject Data Listings

DREAS-1	Discontinued Subjects and Reason for Discontinuation (All Subjects)
SUBEX-1	Subjects Excluded from Analysis Set (All Subjects)
DEMOG-1	Demographic and Baseline Characteristics (All Subjects)
SMED-1	Investigational Medicinal Product Administration (All Subjects)
SMED-2	Predosing (All Subjects)
PDEV-1	Major Protocol Deviations (All Subjects)
AE-1	Adverse Events (All Subjects)
LAB-1	Laboratory Test Results by Subject - Serum Chemistry (All Subjects)
LAB-2	Laboratory Test Results by Subject - Hematology (All Subjects)
LAB-3	Laboratory Test Results by Subject - Urinalysis (All Subjects)
LAB-4	Laboratory Test Results by Subject - Other (All Subjects)
PDATA-1	Inclusion Criteria or Exclusion Criteria Not Met (All Subjects)
PDATA-2	Subject Randomization List (All Subjects)
PDATA-3	Study Completion Status and Reason for Discontinuation (All Subjects)
PDATA-4	Medical History and Complications (All Subjects)
PDATA-5.1	Prior and Concomitant Medications (All Subjects)
PDATA-5.2	Prior and Concomitant Therapy Other Than Medication (All Subjects)
PDATA-6	Physical Examination (All Subjects)
PDATA-7	Vital Signs (All Subjects)
PDATA-8	Weight (All Subjects)
PDATA-9	Electrocardiogram Results (All Subjects)
PDATA-10	Drug-Induced Extrapyramidal Symptoms Scale (DIEPSS) (All Subjects)
PDATA-11.1	Columbia-Suicide Severity Rating Scale (C-SSRS) - Suicidal Ideation and Intensity (All Subjects)
PDATA-11.2	Columbia-Suicide Severity Rating Scale (C-SSRS) - Suicidal Behavior (All Subjects)
PDATA-11.3	Columbia-Suicide Severity Rating Scale (C-SSRS) - Actual Attempts (All Subjects)
PDATA-12	Clinical Global Impression - Severity (CGI-S) (All Subjects)
PDATA-13	Clinical Global Impression - Improvement (CGI-I) (All Subjects)
PDATA-14	Pharmacokinetic Blood Draw Time (All Subjects)
PDATA-15	DNA Storage (All Subjects)
PDATA-16	CYP2D6 Genetic Test (All Subjects)
PDATA-17	Meal (All Subjects)
PDATA-18	Bowel-movement Investigation (All Subjects)
PDATA-19	Post-treatment Follow-up (All Subjects)
PDATA-20	Screen Failures (All Subjects)
PDATA-21	Hospitalization (All Subjects)

A horizontal bar chart illustrating the percentage of the population aged 65 and older across various US entities. The x-axis represents the percentage, ranging from 0% to 25% in 5% increments. The y-axis lists the entities. The bars are dark gray, with the length of each bar corresponding to the percentage value for that entity.

Entity	Percentage (%)
Mississippi	~14
Alabama	~16
Arkansas	~17
Florida	~18
Illinois	~19
Michigan	~20
North Carolina	~21
South Carolina	~22
Washington	~23
Wyoming	~24
District of Columbia	~24
Alaska	~25
Guam	~25
Hawaii	~25
Missouri	~25
Puerto Rico	~25
Virginia	~25
West Virginia	~25

Category	Approx. Sample Count
1	850
2	120
3	120
4	120
5	120
6	120
7	120
8	120
9	120
10	120

This horizontal bar chart displays 10 data series, each consisting of two bars. The first 9 series are set against a light gray background, while the last series is set against a dark gray background. Each bar is black and represents a different data value for each of the 10 series.
